The Mulligan Concept is a manual therapy paradigm used to correct pain of mechanical origin by using specific joint mobilizations with limb movement to restore functional relationships between joint surfaces. The purported benefits of the Mulligan Concept are an immediate reduction or abolition of pain, immediate restoration of function, and options for self-treatment.^{15, 14, 16} The effects of a manual therapy intervention aimed at restoring mechanical and motor control function of the lumbopelvic region have yet to be measured in women with PPGP. The proposed project will improve knowledge surrounding PPGP and create evidence for clinical practice options. If the proposed aims are achieved, we will have a better understanding of the efficacy of the Mulligan Concept for use in the pregnant population, build upon current research associating poor motor control to PPGP, and introduce novel assessment and treatment procedures for women suffering from PPGP.

Innovation

There is growing consensus that the etiology of PPGP is not due to hormonally induced laxity, but a combination of mechanical and motor control dysfunctions.^{3, 5, 8, 12} Researchers have identified gait characteristics and joint relationships differences that are unique to patients with PPGP; not found in pregnant women with out PPGP or in patients with simple low back pain.^{3, 8, 10} Positional abnormalities (e.g., subluxation of the pubic symphysis), changes in gait (e.g., thoracic and lumbar rotation timing and amplitude), and muscle activation patterns have been associated with the syndrome but

not found in matched healthy subjects.^{3, 8,13} Failure of the load transfer mechanism of the sacroiliac joints, specifically, is associated with positional displacements of the joints in pelvic girdle and can cause dysfunctional pelvic girdle movement, loss of motor control, pain and disability.¹⁸⁻²⁰ Researchers have yet to conduct intervention trials to determine whether these associated dysfunctions can be altered with treatment. A clinician utilizing the Mulligan Concept would aim to simultaneously restore the load transfer mechanism and correct the malpositioning of the joints of the pelvis through mobilizations and patient movement. The concept is novel and has yet to be tested in this population. This application seeks to shift current research toward clinical intervention trials that close the evidence-based medicine gap and aim to inform clinical practice.

Approach

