Each participant will then perform a walking gait and sit-to-stand task as a baseline, in the University of Idaho Biomechanics Laboratory. An eight-infrared camera optical system (Vicon Motion Systems Ltd., Oxford, UK) and forceplate (AMTI, Watertown, MA, USA) will be used to collect the kinematic and kinetics data during the tasks. In addition, an eight-channel wireless electromyography (EMG) system (Delays, Inc., Natick, MA, USA) will be used to collect muscle activity during the gait and sit-to-

stand tasks, and the active straight leg raise (ASLR) special test. The participants in the treatment group will receive a Mulligan Concept evaluation and treatment administered by a Certified Mulligan Practitioner. The placebo group will undergo only the Mulligan Concept evaluation. The same tasks and ASLR will be repeated. Outcome measures and physical examination will also be repeated.

The study will be conducted under a randomized triple blinded placebo trial design. Neither the participants, the treating clinician, biomechanist, nor researcher collecting outcome measures will know the group designation of the participants. Conducting the trial in this manner will ensure the lowest possibility that any observed effects of the intervention are due to confounding factors.

Statistical Analysis

Sample size calculations were conducted to determine the appropriate number of participants that must be included. A sample size of 17 participants per group is needed to detect differences between groups with 80% power, and an *a priori* alpha of 0.05. Accounting for a reasonable 5% drop out rate, the final recommended number of participants is 36 (18 participants per group).

Specific Aim #1: Determine if Mulligan Concept manual therapy produces immediate changes in pain and self-reported function in women with PPGP.

A series of independent samples t-tests will be used to determine if a difference exists between the mean scores of the intervention and placebo groups on the VAS, PSFS, ADQ, and PGQ.

Specific Aim #2: Determine whether treatment with the Mulligan Concept immediately restores or alters dysfunctional gait characteristics and pelvic girdle motor control in women experiencing PPGP.

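### The treating clinician is listed among those blinded to group, but the plan's own description of the two arms makes that impossible

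*Combined protocol and SAP*

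**What the plan says.** Everything needed is in the Approach section, with one supporting description in Innovation and one in Statistical Analysis.

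- **Arms (Approach).** "The participants in the treatment group will receive a Mulligan Concept evaluation and treatment administered by a Certified Mulligan Practitioner". For the control: "The placebo group will undergo only the Mulligan Concept evaluation".
- **Repeat measurement (Approach).** After the session the movement tasks are redone, and "Outcome measures and physical examination will also be repeated".
- **Design label (Approach, next paragraph).** "The study will be conducted under a randomized triple blinded placebo trial design".
- **Who is blind (Approach, following sentence).** "Neither the participants, the treating clinician, biomechanist, nor researcher collecting outcome measures will know the group designation of the participants".
- **The assurance drawn from this (Approach).** "Conducting the trial in this manner will ensure the lowest possibility that any observed effects of the intervention are due to confounding factors".
- **What the clinician does (Innovation).** A clinician using the concept aims to restore load transfer and to "correct the malpositioning of the joints of the pelvis through mobilizations and patient movement".
- **Where the comparison is used (Statistical Analysis, Specific Aim #1).** Independent-samples t-tests will "determine if a difference exists between the mean scores of the intervention and placebo groups on the VAS, PSFS, ADQ, and PGQ".

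**The concern.** The plan claims a property for one role that the described procedures rule out. The treatment is manual and the control omits it, so the person giving the treatment cannot be unaware of giving it.

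The claim bears on how the main result is read. Aim 1 asks about immediate changes in pain and self-reported function, and its four scales are completed by the participant. A practitioner who knows the group could affect such scores through manner, encouragement or length of contact. The documents do not show that this would happen, but a blinding statement that includes the practitioner tells readers the route is closed when it is open. The plan then relies on that statement for a broad assurance about confounding. It also says, under plans for future grant applications, that the findings will inform later and larger research, so an incorrect design label would be carried forward.

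**Working it through.** No arithmetic applies, and the plan gives no figure on this point to reproduce. The check sets the arm descriptions beside the blinding sentence, role by role.

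**Step 1. What differs between the arms.** Both receive the evaluation. The treatment group also receives treatment, which Innovation describes as mobilizations with patient movement. The control receives the evaluation only; that wording leaves no room for a sham treatment, and none is described. Delivery of the treatment is thus the stated difference between the arms.

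**Step 2. Each role named as blinded.**

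| Role | Needed for blinding | Position in the documents |
|---|---|---|
| Treating clinician | Must not be able to tell whether treatment was given | Contradicted: this person gives it |
| Biomechanist | Must not see the session or be told the group | Possible; no procedure described |
| Outcome collector | Must not see the session or be told the group | Possible; no procedure described |
| Participant | Must not recognise the evaluation alone as the control | Possible; depends on what participants are told and what the evaluation involves |

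Count: 4 roles named, 1 contradicted.

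**Step 3. Can staffing rescue the claim?** The plan does not say who evaluates the control group. There are two cases.
- One practitioner handles both groups. That person goes on to treat or stops after the evaluation, and so knows the group every time.
- A separate person evaluates the controls. The treater then sees only treatment-group participants, and knows that everyone treated is in that group.

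The treater knows the group in both cases.

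**Step 4. Which results are exposed.** The scales in the Aim 1 tests are VAS, PSFS, ADQ and PGQ. Matched by their initials to the list of primary patient-reported measures in Approach, all 4 of 4 are on it. Aim 2 compares instrument recordings descriptively and is less exposed.

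**Step 5. What the Aim 1 difference contains.** Evaluation plus treatment minus evaluation alone leaves the treatment together with any additional contact and expectation that come with it. The t-test cannot separate these.

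**The case against.** The contradiction itself has no good defence. The fair objections concern how far it reaches.

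*The harm is not specific to the clinician.* With patient-reported scales the more direct route to bias is the participant's own expectation, and the extra contact would be part of the contrast even if the clinician could somehow be blind. This stands. It is why the point is limited to a false statement about one role and what may be claimed from it, and does not assert a demonstrated bias.

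*Aim 1 makes no blinding claim of its own.* It says only that group means will be compared. This also stands. The wording for Aim 1 and for the confounding sentence follows from correcting the blinding sentence; these are not separate errors.

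*The study is exploratory and the remedy changes no outcome, test or sample size.* True, but an incorrect statement of a core design property needs correcting whatever the size of the study.

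A reader might infer three stronger things. None is supported.
- *Participants are certainly unblinded.* An evaluation-only control with no sham makes this a reasonable question. But the content of the information packet is not given, the consent form is not among the documents, and the content of the evaluation is not described.
- *The placebo label is wrong.* This turns on the same missing facts. If the evaluation is hands-on and participants are not told which part is active, it might serve as a placebo.
- *The false-positive rate is inflated by a known amount.* The documents give no bias size. Any figure would come from an assumed bias and would say nothing particular to this trial.

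**Conclusion.** Wrong as written, and it must be corrected. The Approach section states that the treating clinician will not know the group, while its description of the arms ensures that whoever treats does know. The size of the error is one of four named roles. The results most affected are the four patient-reported comparisons in Aim 1.

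The conclusion rests on two readings: that the treatment is the hands-on procedure described in Innovation, and that the control receives nothing beyond the evaluation, as stated. It does not depend on whether one or two people carry out the sessions.

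Blinding of the biomechanist and outcome collector is feasible and not contradicted. Participant blinding is neither established nor refuted. The direction and size of any effect on the scores are unknown.

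**What to change.** **Correction.** Remove the treating clinician from the blinding sentence. Replace the triple-blind label with a statement naming each role that is blinded: the biomechanist, the outcome collector, and participants if the packet and consent wording support it. Say plainly that the treating practitioner is not blinded. A count alone will not do: with the clinician removed three roles remain, so the word triple could survive and hide the change.

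**Consequences of the correction.**
- Qualify the sentence on confounding, so that it claims only what the remaining blinding can deliver.
- Report Aim 1 as evaluation plus treatment versus evaluation alone with an unblinded practitioner, noting that any additional contact and expectation are part of the difference.

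**Requests for detail.**
- What the control evaluation consists of, and why it is expected to work as a placebo.
- What participants are told about the two groups, and how they are kept unaware of their own.
- Who performs the repeat physical examination, and whether that person is blinded.

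**Optional safeguards.** Keep the biomechanist and outcome collector out of the session. If participants are asked to guess their group, report the guesses by group with a caution: the treatment is expected to relieve pain at once, so a correct guess may reflect benefit as well as failed blinding.

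**Cost.** The correction and its consequences are wording only and leave outcomes, tests and sample size unchanged. The price is a less favourable blinding claim. The first safeguard needs a rule on who is in the room, and the second needs one question per participant. Staffing and session length are not given, so any effect on them cannot be judged.

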Twenty pregnant volunteers, ages 20-45 years, will be recruited for the study. Participants will be between their 20th-34th week of gestation, with reported pregnancy-related lumbopelvic pain. Participants would be excluded for any of the following criteria:

- orthopaedic or neurological problems with walking (other than PPGP)
- prior surgery of the lumbar spine, pelvis, hip, or knee
- fracture
- known malignancy
- active inflammation in the lumbar spine or pelvis
- ankylosing spondylitis, Scheuermann's kyphosis, active polyarthritis, or severe osteoporosis
- any pulmonary, cardiac, visual, auditory, or cognitive disorders
- any other multi/co-morbidities that limit the volunteers ability to complete a gait and sit-to-stand task

Volunteers will be recruited from Latah County, Idaho and surrounding areas by word of mouth and print and social media. Pregnant women who express interest in the study will be given an informational packet explaining the methods, risks, and benefits of participation. If the women decide to participate they would sign a consent statement and conduct an initial questionnaire, sent via online link. The survey would be used to determine inclusion and exclusion criteria, and group assignment (i.e., intervention group, placebo group). Un-paired t-tests will be conducted to determine whether significant differences exist between intervention and control groups in age, weight, height, as well as gestational week and number of pregnancies. Randomly stratifying the participants in to groups in this manner minimizes the potential confounding variables.

Participants will report to the University of Idaho Integrated Sport Medicine and Rehabilitative Therapy Clinic for initial patient reported outcome measures collection and standardized examination. Primary patient reported outcome measures include the Visual Analog Pain Scale, the Pelvic Girdle Questionnaire, the Assessment of Disablement Questionnaire, the Patient Specific Function Scale, and the Short Stress State Questionnaire. The examination will include history, palpation, special tests (e.g., Posterior Pelvic Pain Provocation test, Active Straight Leg Raise), and neurological screen.

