The timing and amplitude of lumbar and thoracic spine rotations, as well as muscle activity, will be recorded and compared using descriptive statistics. Between groups analysis will consist of descriptive statistics to compare differences in timing, amplitude, and EMG activity after intervention.

Specific Aim #3: Identify intake factors that predict treatment outcome.

Standard multiple regression and step-wise multiple regression will be used to predict treatment outcome from different factors of interest (e.g., number of pregnancies, week of gestation, initial ADQ score, etc.).

Project Timeline

Preparation for participant recruitment will begin July 15th, 2017. Participant recruitment will take place between December 2017 and March 2018. Data collection will take place over 5-6 days in late March 2018. Data Analysis will take place between April and May 2018. Abstract and manuscript development and preparation for publication and presentation will take place through December 2018.

Interim Milestones

The following interim milestones will be used to hold the PI and research team accountable. These milestones will be shared with the research team and overseen by the PI. When appropriate and if a milestone is not met in a timely fashion, guidance will be sought from the Mentor and a plan for re-establishing the project timeline will be established and implemented.

Phase	Milestone	Timeline
Study Start Up	
 • IRB Approval • Award Announcement • Preparation • Pre-recruitment planning (e.g., creation of media material) 	
 • Prior to March 1, 2017 • May 31, 2017 • July 15- October 1, 2017 • October 1- December 1, 2017
Study Conduct	
 • Ready to Recruit • Materials completely distributed • 50% Enrollment Achieved • 100% Enrollment Achieved • Data Collection 	
 • December 1, 2017 • January 15, 2018 • February 20, 2018 • March 15, 2018 • Late March, 2018
Study Close-out	
 • Attendance at Annual Meeting • Publication within 12 months of study close 	
 • May, 2018 • December, 2018

Plans for developing and submitting future grant applications

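### Aim 1 does not say whether its t-tests compare post-treatment or change scores and states no baseline adjustment, although all four scales are measured before and after treatment

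*Combined protocol and SAP*

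**What the plan says.** Specific Aim #1 (Statistical Analysis) asks whether the therapy "produces immediate changes in pain and self-reported function in women with PPGP". Its whole analysis is: "A series of independent samples t-tests will be used to determine if a difference exists between the mean scores". The comparison is between the two arms on four scales: VAS, PSFS, ADQ and PGQ. No time point, score type or covariate is named.

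The Approach section has these scales measured twice. Participants first attend the clinic for "initial patient reported outcome measures collection and standardized examination". After the evaluation, with or without treatment, "Outcome measures and physical examination will also be repeated".

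A baseline score is named in only one analysis. Specific Aim #3 will "predict treatment outcome from different factors of interest (e.g., number of pregnancies, week of gestation, initial ADQ score, etc". That is a prediction model and does not adjust the Aim 1 group comparison. The baseline comparability t-tests in the Approach section cover age, weight, height, gestational week and number of pregnancies, but none of the outcome scores.

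The documents give two trial sizes. The Approach section says "Twenty pregnant volunteers, ages 20-45 years, will be recruited for the study", which is 10 per group if split equally. The Statistical Analysis section asks for 17 per group, raised to 18 for dropout.

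**The concern.** With a baseline and a post-treatment value for every woman, the Aim 1 sentence can be read in two ways: a t-test on post-treatment scores or a t-test on changes. Under randomisation both estimate the same group difference, but with different precision, and which is more precise depends on the baseline-to-post correlation. A third analysis, ANCOVA on the post-treatment score with baseline as covariate, uses the same data and is usually at least as precise as either.

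Two things are at stake. With 20 to 36 women, the choice can move power a good deal. And if the score type were settled only after the data had been seen, the nominal 5% error rate would no longer hold. The same silence reaches the sample size: the plan does not say which score's SD underlies the 17 per group.

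**Working it through.** **The plan's own figure.** The dropout step reproduces: 17/0.95 = 17.9, so 18 per group and 36 in total. The 17 itself cannot be reproduced, because no effect size, SD, endpoint or sidedness is given. Solved backwards for 80% power at alpha 0.05, 17 per group corresponds to a standardised difference of 0.99 (two-sided t-test) or 0.87 (one-sided).

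**Inputs.** From the documents: alpha 0.05; 17 per group (Statistical Analysis); 10 per group (half of the 20 in the Approach section, assuming equal groups). Assumed, because the documents give no value: true difference d = 1.0 post-score SD, close to the 0.99 above; equal SDs before and after; normal scores; two-sided tests; simple 1:1 randomisation (the stratification mentioned in the Approach section is not modelled); correlation r from 0 to 0.8.

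**Formulas.** Relative to the post-score variance, the variance factors are 1 for post scores, 2(1 − r) for change scores and 1 − r² for ANCOVA. The effective standardised difference is d divided by the square root of the factor.

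| r | change: factor, effective d | ANCOVA: factor, effective d |
|---|---|---|
| 0.3 | 1.40, 0.85 | 0.91, 1.05 |
| 0.5 | 1.00, 1.00 | 0.75, 1.15 |
| 0.7 | 0.60, 1.29 | 0.51, 1.40 |

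Change scores therefore beat post scores only when r exceeds 0.5.

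**Power** (simulation, 100,000 trials per cell):

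| n per group | r | post t-test | change t-test | ANCOVA |
|---|---|---|---|---|
| 10 | 0 | 0.56 | 0.32 | 0.54 |
| 10 | 0.3 | 0.56 | 0.43 | 0.57 |
| 10 | 0.5 | 0.56 | 0.56 | 0.66 |
| 10 | 0.7 | 0.56 | 0.78 | 0.82 |
| 17 | 0 | 0.81 | 0.52 | 0.79 |
| 17 | 0.3 | 0.81 | 0.67 | 0.83 |
| 17 | 0.5 | 0.81 | 0.81 | 0.89 |
| 17 | 0.7 | 0.81 | 0.95 | 0.97 |

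A noncentral-t calculation at d = 0.991 agrees closely. For ANCOVA at r = 0.3, 0.5 and 0.7 it gives 0.84, 0.90 and 0.98 at 17 per group, and 0.59, 0.67 and 0.83 at 10. It runs slightly above the simulation because the formula ignores chance baseline imbalance.

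At r = 0.8, change scores against ANCOVA give 0.916 and 0.926 (10 per group), and 0.994 and 0.997 (17 per group).

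**Expected 95% CI half-width**, in SDs: post scores 0.93 against ANCOVA 0.91, 0.83 and 0.68 at r = 0.3, 0.5 and 0.7 (10 per group); 0.69 against 0.67, 0.61 and 0.50 (17 per group).

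**Disagreement between the two t-tests.** At d = 1.0, one is significant and the other is not in 32, 34 and 38% of trials (10 per group) and 27, 22 and 20% (17 per group) at r = 0.3, 0.5 and 0.7.

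**Type I error if the significant one is reported.** With no effect, P(either) = 0.05 + 0.05 − P(both). The simulated P(either) is 0.089 to 0.094, so P(both) is about 0.006 to 0.011. ANCOVA alone stays at 0.048 to 0.051.

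**Sensitivity.** The Significance section speaks of "an immediate reduction or abolition of pain", so a floor was tried (31% of treated women at the floor). At 10 per group, power was 0.54 for post scores; 0.38, 0.48 and 0.68 for change scores; and 0.56, 0.63 and 0.78 for ANCOVA. The pattern is the same.

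**The case against.** *Aim 1 speaks of changes, so change scores may be what is meant.* This stands as a possible reading. On it, baseline already enters by subtraction. A reader might infer that the plan ignores the baseline scores; the text does not support that while the score type is open. What can be said is that no use of baseline is stated. On this reading the gain from ANCOVA is modest at r = 0.7 and negligible at 0.8 or more, and values that high are plausible for an immediate repeat of the same scale.

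*The trial is randomised, so an unadjusted t-test is unbiased.* The Approach section says "The study will be conducted under a randomized triple blinded placebo trial design", and given that, the objection stands. A reader might infer that the Aim 1 comparison is biased or invalid; it is not, provided allocation is truly random. That proviso is needed because the same section has the intake survey determine group assignment and refers to random stratification without giving the mechanism.

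*The 9% error assumes conduct that the plan does not propose.* This is correct. The figure needs an analyst who runs both tests and reports the significant one. Naming either score in advance would remove it, so it is a reason to fix the score rather than a reason for ANCOVA in particular.

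*The trial is called exploratory.* True, but it still plans tests at alpha 0.05, and the section on future grant applications makes confirmation of the central hypothesis the ground for further investigation.

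*ANCOVA can lose.* It can, slightly. At r near 0 it is behind the post-score test. If treated post scores were 1.5 times as variable and r = 0.7, the change-score test would be ahead by about 0.02 (10 per group) or 0.01 (17 per group).

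**Conclusion.** The point holds as an undefined outcome score together with an available gain in precision. It does not show an invalid test.

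Under the stated assumptions, the gain in power from ANCOVA over post scores is 0.01 to 0.02 at r = 0.3, 0.08 to 0.10 at r = 0.5 and 0.16 to 0.26 at r = 0.7. Over change scores it is 0.14 to 0.16 at r = 0.3, 0.08 to 0.10 at r = 0.5 and 0.02 to 0.04 at r = 0.7. The benefit thus runs from negligible to material, depending on which t-test was intended and on a correlation that the documents do not give. The case for ANCOVA is that it performs close to or better than the better t-test across this range, so neither has to be known beforehand.

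A reader might take the 20 to 38% disagreement to mean that the two t-tests reach contrary conclusions about the treatment. They differ in significance, not in direction, and the figure depends on an assumed true effect of 1.0 SD; with no effect it is about 8 to 9%.

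This should be settled before analysis. It is an inexpensive improvement, and the randomised comparison is sound without it.

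**What to change.** Before analysis, amend the text under Specific Aim #1. For each of the VAS, PSFS, ADQ and PGQ, name the post-treatment score as the outcome, analyse it by ANCOVA on group and that scale's own baseline score, and report the adjusted mean difference between groups with a 95% CI.

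This needs no new data or visits: a few lines of SAP wording and one degree of freedom per model. If r is near 0, the loss of power against the post-score t-test is about 0.03 at 10 per group (0.56 to 0.54 after rounding) and 0.01 at 17 per group (0.81 to 0.79 after rounding).

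### Aim 1 is tested without any allocation factor although the plan speaks of stratifying; if the groups really are balanced on prognostic factors, the t-test intervals are too wide, and otherwise precision is merely forgone

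*Combined protocol and SAP*

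**What the plan says.** On allocation, the Approach section states: "The survey would be used to determine inclusion and exclusion criteria, and group assignment (i.e., intervention group, placebo group"). It then plans a baseline comparison, with number of pregnancies as a fifth variable: "Un-paired t-tests will be conducted to determine whether significant differences exist between intervention and control groups in age, weight, height, as well as gestational week". The next sentence reads: "Randomly stratifying the participants in to groups in this manner minimizes the potential confounding variables". No strata, cut-points, blocks or minimisation rule are given. The later paragraph on design calls the trial randomised and adds nothing about strata.

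On analysis, Statistical Analysis, Specific Aim #1 states: "A series of independent samples t-tests will be used to determine if a difference exists between the mean scores". The scales compared are the VAS, PSFS, ADQ and PGQ. No covariate or stratum is mentioned. Intake factors enter a model only under Specific Aim #3, as possible predictors of outcome ("e.g., number of pregnancies, week of gestation, initial ADQ score, etc").

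On size, the sample size paragraph asks for 17 per group at 80% power and alpha 0.05, and then: "Accounting for a reasonable 5% drop out rate, the final recommended number of participants is 36 (18 participants per group"). The Approach section instead opens with: "Twenty pregnant volunteers, ages 20-45 years, will be recruited for the study".

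**The concern.** The analysis should reflect the allocation. When groups are made alike by design on a factor that predicts outcome, that factor can no longer drive the groups apart by chance, so the true variance of the difference in means falls. An independent-samples t-test does not know this. It leaves the factor's variation in the within-group error and reports a standard error as if the groups could still differ on it. The interval is then too wide and the test rejects less often than 5% under the null.

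The plan speaks of stratifying, lists two of the same variables as candidate predictors under Aim 3, and leaves all of them out of Aim 1, which holds its only formal treatment comparison (Aim 2 is descriptive). With 20 or 36 women, lost precision matters, because the result is meant to inform whether a larger trial is warranted. This point is separate from adjusting for the baseline score of each scale.

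**Working it through.** **The plan's own figure.** No effect size or SD is stated, so the 17 per group cannot be reproduced directly. Solving the noncentral t for 80% power, two-sided 0.05, n = 17 per group gives a standardised difference of 0.99 (0.87 if one-sided). The dropout step does reproduce: 17 / 0.95 = 17.9, rounded up to 18 per group, 36 in total. The 20 women in the Approach section would be 10 per group if split equally.

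**Assumption.** R² is the share of outcome variance explained by the allocation factor or factors. The documents do not give it. I use 0, 0.1, 0.2 and 0.3.

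**Standard error under exact balance** (outcome SD = 1, n per group):
- SE reported by the t-test ≈ √(2/n)
- true SD of the difference = √(2(1 − R²)/n)
- ratio = 1/√(1 − R²) = 1.00, 1.05, 1.12, 1.20 for R² = 0, 0.1, 0.2, 0.3

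At n = 17 and R² = 0.3: √(2/17) = 0.343 against 0.343 × √0.7 = 0.287. Simulation gave a mean reported SE of 0.341 and a true SD of 0.287, about 19% too wide.

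**Type I error under exact balance.** Approximately P(|T| > 2.037/√(1 − R²)) with 32 df, where 2.037 is the two-sided 5% critical value:
- R² = 0.1: threshold 2.147, about 4.0%
- R² = 0.2: threshold 2.277, about 3.0%
- R² = 0.3: threshold 2.435, about 2.1%

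Simulation (40,000 trials per cell) gave 3.9%, 3.1% and 2.2%, and 5.0–5.2% for the adjusted model.

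**The point estimate.** In a simulation balanced within two strata (18 per group, R² = 0.3), the empirical SD was 0.276 for the unadjusted difference and 0.274 for the adjusted one. The estimate keeps the balance. Only the SE, test and interval miss it.

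**Power at 0.99 SD.** For the adjusted model under exact balance, noncentrality = 0.99 × √(n/2)/√(1 − R²) with 2n − 3 df. At n = 17, R² = 0.3: 0.99 × √8.5 = 2.886, divided by √0.7 gives 3.45, hence 92%. At n = 10: 0.99 × √5 = 2.214, divided by √0.7 gives 2.65, hence 70%.

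Simulated results for R² = 0.1 / 0.2 / 0.3, one factor in the adjusted model:

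| Allocation | t-test type I error, 17 per group | Power, 17 per group: t-test | Power, 17 per group: adjusted | Power, 10 per group: t-test | Power, 10 per group: adjusted |
|---|---|---|---|---|---|
| Exactly balanced | 4 / 3 / 2% | 81 / 83 / 84% | 84 / 88 / 92% | 55 / 56 / 57% | 59 / 65 / 70% |
| Continuous factor split at its median into two strata | 4 / 4 / 3% | 81 / 81 / 81% | 83 / 85 / 87% | 55 / 56 / 56% | 58 / 62 / 64% |
| Simple randomisation | about 5% throughout | 80% | 82–83 / 87 / 90–91% | 55% | 57 / 61–62 / 68% |

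For simple randomisation, the t-test's type I error lay between 4.8% and 5.3% for R² from 0 to 0.3, at both sizes.

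**At R² = 0.** Adjustment gains nothing. One factor costs less than 1 point of power under exact balance and about 1 to 3 points under simple randomisation.

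**All five factors.** At 10 per group these take 5 of 18 residual degrees of freedom. At 1.0 SD, R² = 0 and perfect balance, power is 54% against 56% for the plain t-test.

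**The case against.** The strongest objection is that stratification may not take place at all. The five variables are listed for baseline significance tests, not as strata, and the sentence on stratifying can equally describe randomisation followed by a check of the groups. Under simple randomisation the t-test is valid. This stands, so a reader who infers that the Aim 1 standard errors simply are too wide goes further than the documents allow.

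A reader might also infer that the balance is thrown away. It is not: the difference in means keeps it, as shown above.

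Nor does Aim 3 establish that gestational week and number of pregnancies predict outcome. They are candidates, and whether they predict is the question Aim 3 asks. R² could be close to zero, where the effect vanishes. Real strata are also coarse, which brings the test nearer to 5%.

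Finally, any error is conservative, the documents call the trial exploratory, and the conflict between 20 and 36 women costs far more: at 0.99 SD, power falls from 80% to 55%. That is true and limits the weight of this point. It does not remove it. The stated design and the stated analysis still do not match, and one well-chosen factor improves power under either kind of allocation if R² is 0.1 or more.

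**Conclusion.** The point holds in conditional form, as a cheap improvement rather than a threat to validity. The plan claims stratification without defining it and then analyses Aim 1 as if there were none.

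- **If allocation is balanced on prognostic factors:** the t-test is conservative. With 17 per group, type I error is about 4%, 3% or 2% at R² of 0.1, 0.2 or 0.3 under exact balance, and about 3% at R² of 0.3 with two-level strata. At R² of 0 it is 5%.
- **If allocation is simple randomisation:** the t-test is valid, and the only loss is precision that a prespecified covariate could have given.
- **In either case, for R² of 0.1 to 0.3:** adjustment for one factor adds about 2 to 11 points of power at 17 per group and about 2 to 14 at 10 per group, depending on R² and on how allocation is done.

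These sizes rest on an assumed R² and on an effect of 0.99 SD back-solved from 17 per group, two-sided. Neither figure is in the documents. Nothing here inflates false positives or biases the estimate.

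**What to change.** State how participants are allocated and name the factors used. Choose one or two, for example gestational week and number of pregnancies, and use the same ones in allocation and in analysis. Then replace the Aim 1 t-tests with wording such as: each scale will be analysed by a linear model with group and the allocation factors as terms, and the adjusted difference between groups will be reported with its 95% confidence interval.

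The cost is a sentence or two of text and one or two degrees of freedom. If the chosen factors turn out not to predict outcome, the loss is up to about 1 to 3 points of power. Do not enter all five variables in groups this small.
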